## PROTOCOL SYNOPSIS

Title	An Open Label Evaluation of the Adrenal Suppression Potential and Pharmacokinetic Properties of Twice Daily Halobetasol Propionate Foam, 0.05% in Subjects 12 to Less Than 18 Years of Age with Plaque Psoriasis Receiving Two Weeks of Treatment
Study Type	Phase 4 in the United States (US) sites, Phase 2 in the non-US sites, as necessary.
Test Article	Halobetasol Propionate (HBP) Foam, 0.05%
Study Objective	The objective of this study is to determine the adrenal suppression potential and the pharmacokinetic (PK) properties of HBP Foam, 0.05% applied twice daily in subjects who are 12 to less than 18 years of age with stable plaque psoriasis.
Study Design	An open label, multicenter study.
Treatment Groups	All subjects will receive HBP Foam, 0.05%.
Duration of Treatment	Up to two weeks.
Duration of Study	Participation in the study is a minimum of five weeks (at least 20 days between Screening and Baseline Visits, up to two weeks of treatment, and potential follow-up for any subjects who have evidence of hypothalamic-pituitary-adrenal [HPA] axis suppression).
Study Population	Male and female subjects 12 to less than 18 years of age with stable plaque psoriasis.
Total Number of Subjects	Subject enrollment will continue until at least 20 subjects with both Screening and End of Study (EOS) serum cortisol data (pre- and post-cosyntropin stimulation) have completed the study without any significant protocol violations (evaluable subjects). This may require the enrollment of approximately 25 subjects.
Number of Sites	Approximately 12 sites in the US and Europe will participate in the study.
Inclusion Criteria	To enter the study, a subject must meet the following criteria: 

1. Subject is male or non-pregnant female and is 12 to less than 18 years of age (i.e., at least 12 years old, but not yet reached their 18th birthday at the time of enrollment).

2. Subject has provided written informed assent and was accompanied by the parent or legal guardian at the time of assent/consent signing. The parent or legal guardian has provided informed consent for the subject. If a subject becomes 18 years of age during the study, the subject must provide written informed consent at the next study visit to continue study participation.

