Study Procedures	
The following procedures will take place according to the visit schedule:
 
Visit 1 (Screening Visit) (Day -20 or longer): At Visit 1 (Screening Visit), study procedures will be explained by the study coordinator and the subject must provide written informed assent and be accompanied by the parent or legal guardian at the time of assent/consent signing. The parent or legal guardian must provide informed consent for the subject. Consent/assent must be signed prior to the initiation of any study-related procedures. At this visit, consenting/assenting subjects will have their demographics and medical history, including concomitant medications, recorded and Inclusion/Exclusion (I/E) criteria, including percent BSA affected with disease, reviewed to determine subject eligibility. Subjects requiring a wash-out period will be asked to return to complete the following procedures of Screening Visit (Part B) once the wash-out is completed. All female subjects must have a negative UPT to be eligible for this study. Vital signs, height and weight, as well as IGA score, will be recorded. Blood and urine samples will be taken for clinical laboratory tests (chemistry, hematology, and urinalysis). Subjects will have a Screening CST that will be initiated between 7 to 9AM to determine their adrenal system response. A Screening PK sample for drug concentration in plasma will be collected in all subjects in conjunction with the Screening CST. Any adverse events (AEs) will be recorded. Enrollment into the treatment phase of the study (Baseline Visit) should be timed such that the Screening CST will be performed a minimum of 28 days before the projected end of the study phase. To accommodate this requirement, the Baseline Visit should ideally be scheduled at least 20 days

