	
the overall or “average” degree of severity taking into account all of the subject’s psoriatic lesions in the Treatment Area (excluding those on the face, scalp, groin, axillae and other intertriginous areas) by the investigator or designee. This evaluation takes into consideration the three individual characteristics of psoriasis (plaque elevation, scaling, and erythema) with the IGA score at each visit representing the average of plaque elevation, scaling, or erythema that is present amongst all of the lesions eligible for treatment.
 
Percent Body Surface Area Affected with Disease: The percent BSA affected with psoriasis in the Treatment Area (excluding the face, scalp, groin, axillae, and other intertriginous areas) will be estimated at the Screening Visit, Baseline Visit/Day 1, Day 8, and Day 15.
 
Percent Body Surface Area Treated with Test Article: The percent BSA treated with the test article will be estimated at Baseline Visit/Day 1 and Day 8 (for subjects who have not cleared).
 
Test Article Compliance: Subjects will apply the first dose of test article to all plaques within the Treatment Area under staff supervision. At each visit, subject diaries will be reviewed to determine test article doses taken since the last visit and subjects will be counseled regarding compliance if necessary. Subjects will be instructed to record the date that the last dose was applied. All dispensed canisters of test article will be weighed at each visit.
 
Local Skin Reactions: At each visit, subjects will be evaluated for the presence of any LSRs associated with the topical application of corticosteroids including telangiectasia, skin atrophy, burning/stinging, and folliculitis. Burning/stinging will be evaluated post-application at Baseline Visit/Day 1 and Day 8 (for subject who have not cleared).
 
Adverse Events: All AEs will be recorded. At each visit after the Baseline Visit/Day 1, subjects will also be questioned specifically about the status of any ongoing AEs.
 
Clinical Laboratory Tests Urine and blood samples will be collected from each subject for safety laboratory analysis at Visit 1/Screening, Visit 2/Baseline (if applicable), and Visit 4/EOS. Any new or worsening clinically significant abnormalities at Visit 4/EOS will be recorded as AEs.
 
Cosyntropin Stimulation Test: The EOS visit (i.e., the end of the assigned treatment period) should be scheduled in the morning so that the CST will occur at the same time (<math>\pm</math> one hour) as the CST performed at Visit 1 (Screening). The Screening CST will be initiated between 7 and 9AM; all follow-up CSTs should, to the extent possible, be initiated between 7 and 9AM.

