	
determined for the total amount of test article used and average amount of test article used per application by each subject.
 
An approximation of the amount of test article applied per cm^2 will be determined based on the average amount of test article used per application and an estimate of the percent BSA treated with the test article at Visit 2/Baseline. The BSA treated with test article (in square centimeters) will be determined from the Mosteller calculation [1].
 
Urine Pregnancy Tests A listing of UPT results will be prepared.
 
Local Skin Reactions The frequency distributions of the severities of LSRs associated with topical application of corticosteroids including telangiectasia, skin atrophy, burning/stinging, and folliculitis will be summarized at Baseline and all follow-up visits.
 
Adverse Events All subjects enrolled in the study who were dispensed and applied test article at least once will be included in the safety analyses (Safety population). All AEs reported during the study will be listed, documenting onset, whether therapy was required, any change in test article dosing, severity, possible relationship to test article, and outcome. Verbatim terms on the electronic case report forms (eCRFs) will be linked to preferred terms (PTs) and system organ class (SOC) using the Medical Dictionary for Regulatory Activities (MedDRA) mapping system. All reported AEs will be summarized by the number of subjects reporting AEs, SOC, PT, severity, and relationship to test article.
 
Clinical Laboratory Tests Clinical laboratory tests will be evaluated for any clinically significant changes during the study period. All laboratory data (hematology, chemistry, and urinalysis) will be listed and reported in the units received by the laboratory. Shift tables by analyte and by out of range flag will be presented to facilitate the evaluation of change from Visit 1/Screening to Visit 4/EOS.
 
HPA Axis Suppression Analysis HPA axis responses to CST will be dichotomized to normal and abnormal. An abnormal HPA axis response (HPA suppression) is defined as a 30-minute post-stimulation serum cortisol level of <math>\leq 18</math> <math>\mu</math>g/dL at the end of study. The proportion of subjects manifesting laboratory evidence of adrenal suppression at the end of study will be summarized. The mean increases in serum cortisol levels after stimulation will also be summarized at the end of study. In addition, descriptive statistics for the daily dose of test article will be tabulated separately for suppressed and non-suppressed subjects. Post-treatment follow up data will be summarized for subjects determined to have laboratory based evidence of adrenal suppression at the end of study or early termination visit.

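### The AE summary has no onset rule, so AEs recorded before the first application can enter the tables for the foam

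*Combined protocol and SAP*

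**What the plan says.** All references are to the Protocol Synopsis.

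- **Summary rule** (Statistical Methods, Adverse Events): "All reported AEs will be summarized by the number of subjects reporting AEs, SOC, PT, severity, and relationship to test article". The paragraph does not mention treatment-emergent events or a split at the first dose.
- **Listing rule** (same paragraph): "All AEs reported during the study will be listed, documenting onset". Onset is therefore collected.
- **Who is counted** (same paragraph): the Safety population, meaning subjects who applied the foam at least once. This restricts the subjects and not the time of the event.
- **When recording starts** (Study Procedures, Visit 1): "Any adverse events (AEs) will be recorded". Study Measurements adds, without a start date, "All AEs will be recorded".
- **Length of the lead-in** (Duration of Study): "at least 20 days between Screening and Baseline Visits, up to two weeks of treatment". The Visit 1 text is softer: "the Baseline Visit should ideally be scheduled at least 20 days" after Screening.
- **Follow-up** (Study Procedures): only subjects with adrenal suppression at EOS return, at intervals of at least 28 days, until the response is normal. The others leave after a normal CST. The procedures at these visits are referred to Section 9.3, which is not in the text available for this review.

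**The concern.** An AE table in a single-arm safety study is read as what happened to subjects on the product. No control arm shows how much of it is background. Here the rule admits every reported AE, and the stated lead-in is longer than the treatment course.

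Pre-dose events are plausible. Screening includes blood draws and a CST. The exclusion criteria then keep subjects off topical and systemic corticosteroids until treatment starts, and off other topical psoriasis therapy for the 14 days before it. A procedure-related event or a flare in that interval, in a subject later dosed, would be counted under the rule as written.

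Other safety data in the same section are tied to time points: local skin reactions by visit, laboratory results as shifts from Screening to EOS. The AE summary is not. With about 25 subjects, each one wrongly counted moves the incidence by 1/25 = 4 percentage points.

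**Working it through.** **1. The plan's own figure.** The only stated figure that bears on the AE window is the minimum participation of five weeks, or 35 days. The components give 20 pre-dose days + 14 treatment days = 34 days, which agrees to within one day.

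**2. Calendar time before dosing.**
- Two-week course: 20/34 = 59%.
- Exit at Day 8: 20/(20 + 7) = 20/27 = 74%.

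These are shares of calendar time. They equal shares of AE capture only if events are sought equally before and after dosing.

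**3. Direction.** A subject with a treatment-emergent AE is counted under either rule. A subject whose only AE arose before dosing, and did not worsen afterwards, is counted only under the rule as written. So the count under the written rule is equal or higher.

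**4. Size, constant rate.** The documents give no AE rate. Assume a background rate r per subject-day, no drug effect and equal capture throughout. Then P(at least one AE in d days) = 1 − exp(−r × d).

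| r (assumed) | 14 days | 34 days | Ratio | Extra subjects of 25 |
|---|---|---|---|---|
| 0.002 | 2.8% | 6.6% | 2.38 | 1.0 |
| 0.005 | 6.8% | 15.6% | 2.31 | 2.2 |
| 0.01 | 13.1% | 28.8% | 2.21 | 3.9 |
| 0.02 | 24.4% | 49.3% | 2.02 | 6.2 |

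As r falls, the ratio approaches 34/14 = 2.43.

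**5. Size, higher rate on treatment.** Let the on-treatment rate be m times background. The treatment-emergent share is 1 − exp(−14mr) and the all-AE share is 1 − exp(−14mr − 20r).

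| m (assumed) | r (assumed) | Treatment-emergent | All AEs | Ratio |
|---|---|---|---|---|
| 2 | 0.002 | 5.4% | 9.2% | 1.68 |
| 2 | 0.005 | 13.1% | 21.3% | 1.63 |
| 2 | 0.01 | 24.4% | 38.1% | 1.56 |
| 5 | 0.002 | 13.1% | 16.5% | 1.26 |
| 5 | 0.005 | 29.5% | 36.2% | 1.23 |
| 5 | 0.01 | 50.3% | 59.3% | 1.18 |

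If no AE is recorded before dosing, the ratio is 1.

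**6. Unequal observation.** A suppressed subject with one follow-up visit is in the study for at least 20 + 14 + 28 = 62 days, against 34 for a non-suppressed subject. Whether AEs are recorded in the last 28 days cannot be seen without Section 9.3.

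**The case against.** **Pre-dose capture may be thin.** The Visit 2 text describes AE recording only after the application. For the interval since Screening, it has staff reconfirm medical history and update concomitant medications. Specific questioning about ongoing AEs begins only after Baseline. This stands as a limit on size: the equal-capture model in steps 4 and 5 may overstate the effect. It does not remove the problem, because Visit 1 records AEs and the general instruction in Study Measurements has no start date.

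**The tables already break AEs down by relationship, and the listing shows onset.** A pre-dose event cannot be caused by the foam, and a reader could pick such events out of a listing of about 25 subjects. This helps in part. The overall, SOC, PT and severity counts would still be mixed, and relationship is an open-label judgment.

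**The available text is a synopsis.** It points to sections that are not in it, and a treatment-emergent definition could stand elsewhere. That is a fair caution. However, the synopsis states a positive rule covering all reported AEs; if a narrower rule exists elsewhere, the two need to be aligned.

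**Stronger readings that a reader might infer.**
- *That AE incidence is overstated, and about two-fold.* No AE rate is given. The two-fold result needs no drug effect and equal capture before dosing, and neither is documented.
- *That follow-up of suppressed subjects inflates the same tables.* AE recording at those visits is not shown, and AEs after EOS in these subjects may be real drug effects, so counting them is not in itself overstatement. What the documents do support is unequal observation time.

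**Conclusion.** The concern holds as a defect in the rule, with a known direction and an unknown size. Pre-dose AEs in dosed subjects can enter the AE tables and can never lower the number of subjects with an AE. For a two-week course with a 20-day lead-in, the assumed rates give anything from no change to about 2.4-fold. The upper end, about 1 to 6 extra subjects of 25, rests on a constant background rate of 0.002 to 0.02 per day with equal capture before and during treatment. A fivefold on-treatment rate brings the ratio down to 1.18 to 1.26. This range is not a strict bound: a longer lead-in or an exit at Day 8 would raise the ratio for that subject, and the documents do not say how many such subjects to expect.

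The effect is confined to the descriptive AE incidence. No between-arm comparison exists to be biased, and the HPA and PK endpoints are unaffected. The change is still worth making, because AEs are a named safety endpoint, this is their only planned summary, and the data needed are already collected.

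**What to change.** Replace the summary rule with wording such as:

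> *A treatment-emergent AE is one that begins, or worsens in severity, on or after the first application of test article. The tables by SOC, PT, severity and relationship will present treatment-emergent AEs up to the EOS visit. AEs that begin before the first application and do not worsen afterwards will be listed separately. Any AEs recorded in post-treatment follow-up of suppressed subjects will be summarized in a separate table, with the number of subjects followed as the denominator.*

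State how an event on Day 1 is classified if its time relative to the application is unknown; counting it as treatment-emergent is the cautious choice.

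Follow-up AEs should not be cut off at EOS and left to listings alone. They arise in the subjects of most interest for adrenal suppression, and dropping them from the summaries could hide delayed effects. They need their own table because the other subjects are not observed over that time.

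The cost is one derived onset flag and a small extra table or listing. No new data, visits or subjects are needed.
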